8.4 Tissue Prioritization

We anticipate that the biopsies will provide sufficient tissue for all the studies to be performed above. One good core of tissue should be sufficient for all the IHC stains, and one good core should be sufficient for the NGS. However, should there be insufficient tissue, the priority will be as follows:

- The IHC will take priority, with the specific priority order following the order of markers listed above (a through g)
- The NGS will be the second priority. For the NGS, there is no “priority” order of the genes analyzed, as the entire panel will be run at once.

9.0 STATISTICAL CONSIDERATIONS

9.1 Objectives:

9.1.1 Primary Objective of the Phase I Portion:

To determine the Recommended Phase II dose (RP2D) of LEE011 in the combination with everolimus in patients with mPAC refractory to 5-FU- and GEM-based chemotherapy

9.1.2 Primary Objective of the Phase II Portion:

To determine the progression-free survival (PFS) rate at 8 weeks (PFS_{8 weeks}) to assess the clinical efficacy of the combination of LEE011 and everolimus in patients with mPAC refractory to 5-FU- and GEM-based chemotherapy

9.1.3 Secondary Objectives

9.1.3.1 To determine the mPFS of patients treated with the combination of LEE011 and everolimus in patients with mPAC refractory to chemotherapy

9.1.3.2 To determine the mOS of patients treated with the combination of LEE011 and everolimus in patients with mPAC refractory to chemotherapy

9.1.3.3 To determine the best ORR, the largest percent decrease in tumor size from baseline as measured by expert radiologists using RECIST v1.1 criteria, defined as the proportion of patients with a CR or PR, of the combination of LEE011 and everolimus in patients with mPAC refractory to chemotherapy

9.1.3.4 To determine the safety and tolerability of the combination of LEE011 and everolimus in patients with mPAC refractory to chemotherapy

9.1.4 Exploratory Objectives

9.1.4.1 To correlate the PFS_{8 weeks} to correlative scientific markers, including the analysis of tumor biopsies and blood-based markers, including RB, pRB, p16, cyclin D1, Ki67, MCM7, and pS6 levels by immunohistochemistry

9.1.4.2 To screen for use a targeted sequencing approach for genetic lesions observed in pancreatic cancer that includes KRAS, SMAD4, TP53, CDKN2A as well as other commonly mutated cancer genes

9.1.4.1 To assess blood for the analysis of circulating tumor DNA as a surrogate marker of disease burden. KRAS and other mutations will be used as the determinants of tumor selective DNA

9.2 Study Design

This study is a single-arm, open-label, Phase I/II trial of the combination of LEE011 and everolimus in refractory mPAC. The Phase I portion of the trial will be conducted in a 3+3 design, enrolling patients in cohorts of 3 patients each. If 0-1 DLTs occur in a cohort of 3 patients, the cohort will be expanded to 6 patients. If 0-1 DLTs occur in the group of 6 patients, the RP2D will be that dose level. Otherwise, 3 patients will be enrolled at the next lowest dose level and the process continued until the RP2D is determined (0-1 DLTs within the 6 patients at that dose level) or the study is terminated (if there are 2 or more DLTs at Dose Level -3).

The Phase II study will be conducted using a Simon's Minimax two-stage design. In the initial stage 11 patients will be enrolled, and if at least 3 patients are progression-free at 8 weeks, then an additional 15 patients will be enrolled in the second stage for a total of 26 patients on study. If 2 or fewer patients are progression-free at 8 weeks, then the study will be terminated for futility. 3 additional patients will be screened and may be used to replace up to 3 of the 26 patients,

provided those initial patients undergo screening but do not start study treatment within 3 weeks of screening. Thus, a total of 29 patients are expected to be screened for the Phase II portion of this study.

9.3 Sample Size Considerations

Using a Simon Minimax 2-stage design with a null hypothesis of 25% and an alternative hypothesis of 50% (or greater) a total of 26 evaluable patients are needed (assuming 90% power and $\alpha=0.1$ (one-sided)).

For the Phase I portion, there may be as few as 12, and as many as 18 patients enrolled strictly in the Phase I portion (and not treated at the RP2D of LEE011, thus not counted towards the Phase II portion of the study). Thus, as many as 44 patients may be accrued for this trial. Anticipating an accrual rate of 3 patients per month, the trial is expected to complete accrual in approximately 15 months.

9.4 Endpoints

9.4.1 Primary Endpoint

PFS at 8 weeks is a complete response (CR), partial response (PR), or stable disease (SD) by imaging study (CT or MRI), evaluated by expert radiologists using RECIST v1.1 criteria, at the 8 week response assessment. Each patient will be categorized as either success/failure for being progression free at 8 weeks.

9.4.2.5.1 RB, defined as positive if any tumor cells have RB nuclear staining

9.4.2.5.2 pRB, defined as positive if any tumor cells have phosphorylated-RB nuclear staining

9.4.2.5.3 p16, defined as positive if nuclear staining in 5% or more of tumor cells

9.4.2.5.4 Cyclin D1, defined as positive if any tumor cells have cyclin D1 nuclear staining

9.4.2.5.5 Ki67, defined as a percentage of positively stained cells (nuclear staining and mitotic figures) among the total number of malignant cells viewed in at least 3 randomly-selected high-power (x40 objective) fields

9.4.2.5.6 MCM7, defined as a percentage of positively stained cells (nuclei) among the total number of malignant cells viewed in at least 3 randomly-selected high-power (x40 objective) fields

9.4.2.5.7 pS6 (Ser235/236) defined using a histoscore of intensity and percent of tumor cells staining

9.4.2.6 Frequency of mutations from targeted NGS analyses from pre-treatment biopsy specimens will be ranked.

9.4.2.7 ctDNA will be collected via serial blood samples with frequency as described above and quantitatively measured, defined as the number of mutant fragments in 5 mL by quantitative PCR.

9.5 Analysis Plan

9.5.1 Analytic plan for primary objective

The null hypothesis is that the PFS rate at 8 weeks is 25% (based on historical controls wherein third-line therapy in mPAC revealed stable disease in 25-31% of patients^{5,6}.) versus an alternative hypothesis that the rate is 50% or higher. The plan is to use a Simon's Minimax two-stage design with 11 patients enrolled during the first stage. If 3 or more (out of 11) patients are progression free the trial will continue with an additional 15 patients being enrolled during the second stage (for a total of 26 patients). If 10 or more patients are progression free at 8 weeks the trial will declare that the intervention has met the pre-specified criteria for success.

9.5.2 Analytic plan for secondary objectives

9.5.2.1 Survival and response endpoints:

9.5.2.1.1 The nonparametric Kaplan-Meier method will be used to estimate median PFS.

9.5.2.1.2 The nonparametric Kaplan-Meier method will be used to estimate median OS.

9.5.2.1.3 We plan to determine the ORR within a $\pm 20\%$ range based on our sample size.

9.5.2.2 Adverse event data will be compiled and tabulated using descriptive statistics.

9.5.2.3 Pharmacodynamic analyses are exploratory, but we hypothesize that proliferation indices (Ki67 and MCM7) will be decreased in the on-treatment sample compared to the pre-treatment sample and could correlate with PFS. Similarly, expected decreases in levels of pRB, cyclin D1, p16, and increases in RB could correlate with PFS. Cox proportional hazard regression models will be fit to determine whether these secondary endpoints are associated with PFS.

9.5.2.4 NGS analysis is also exploratory in nature. Using results from these analyses will examine whether median PFS is different with patients with mutations in *CDKN2A* compared to those without these mutations.

9.5.2.5 ctDNA studies are exploratory and overall trends in serial measurements may support a response (or lack of response) signal to treatment and could be correlated with PFS as a surrogate marker of disease burden.

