
	
Trial Auditing
 
The multi-institutional coordinator will arrange all primary source documents for the patients to be audited. This will include collecting copies of the primary source data for any patients treated at other sites.

Statistical Design, Feasibility, and Trial Duration
	
This is a multi-institutional single arm, open label Phase I/II study to evaluate the PFS_{8weeks} of the combination of LEE-011 plus everolimus, in patients with metastatic pancreatic cancer refractory to 5-fluorouracil (5-FU) and gemcitabine-based chemotherapy. Previous studies of third-line therapy in mPAC are limited but reveal stable disease in 25-31% of patients with no partial or complete responses (31% of patients in the GVAX/CRS-207 combination vaccine study had stable disease but only 52% of these patients were treated in the third-line setting)^(5, 6). It is hoped that the combination of LEE-011 plus everolimus can increase the PFS_{8weeks} to at least 50%, though early stopping rules are in place for lack of efficacy.
 
All patients meeting the eligibility criteria and who have signed a consent form, have begun treatment, are not lost to follow-up, and are not taken off study for reasons other than progression or death before 8 weeks will be considered evaluable for the assessment of the DCR.
 
Between 12 and 24 patients will be enrolled in the Phase I portion of the study, depending on whether DLTs occur and dose de-escalation is required. The 6 patients treated at the RP2D will be included in the Phase II portion of the study. We anticipate the combination will be well tolerated such that all of the patients in the Phase I portion are likely to be evaluable for the Phase II efficacy analysis.
 
26 evaluable patients will be enrolled in the Phase II portion of the study (though the potential drop-out rate is 10%), which will provide a 90% power to detect an improvement in the DCR from 25% (based on historical control) to 50%, assuming a 1-sided significance level of 0.1 and an accrual rate of 2 patients per month. A Simon's optimal two-stage design will be used to test the null hypothesis that the DCR $P \leq 0.25$ versus the alternative that $P > 0.5$. For the first stage, 11 patients will be entered to the study. The trial will be terminated if 2 or fewer patients achieve a PR, CR, or SD at 8 weeks. If at least 3 patients in the first stage achieve a PR, CR, or SD at 8 weeks, the trial goes on to the second stage. A total of 26 patients will be enrolled. If the total number of patients who achieve a PR, CR, or SD at 8 weeks is less than or equal to 9, the combination therapy will be rejected. If however, 10 or more patients achieve a PR, CR, or SD at 8 weeks the combination therapy will be considered for further analysis.
 
With 26 evaluable patients in the Phase II portion, combined with a minimum of 12 to a maximum of 18 patients enrolled strictly in the Phase I portion of the trial, there will be up to 44 patients enrolled. At an expected accrual rate of 3 patients per month, the expected accrual duration will be approximately 15 months.
 
Descriptive statistics will be used to summarize patients' demographics, toxicity, and quality of life. The PFS_{8weeks} will be estimated from the observed data with 95% exact binomial confidence interval. The nonparametric Kaplan-Meier method will be used to estimate the survival function and calculate the PFS and OS. The ORR will be estimated from the observed data with 95% exact binomial confidence intervals.

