4.4.8 Imaging and Response Evaluation

Patients will undergo a baseline tumor evaluation with imaging studies within 3 weeks prior to Cycle 1 Day 1. Imaging studies should include a diagnostic CT scan of the chest, abdomen, and pelvis with PO and IV contrast (unless medically contraindicated). If a patient has an allergy to IV contrast, appropriate pre-medication can be given to prevent a contrast reaction. Patients may undergo other modalities such as an MRI instead of a CT scan at the treating physician's discretion if appropriate (such as severe allergy to CT contrast, extremity tumors, bone metastases requiring bone scans, etc.).

Response evaluation will occur every 8 weeks (regardless of treatment cycle) and at the final visit, if not performed within the last 4 weeks. Tumor response and/or disease progression will be assessed by the modality(ies) used prior to treatment. Patients will continue to remain on study as long as there is no evidence of PD and the therapy is adequately tolerated.

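### With scans every 8 weeks, a Kaplan-Meier median PFS near 8 weeks would not separate the null from the alternative, and under the null it is biased upward

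*Combined protocol and SAP*

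**What the plan says.** Section 9.5.2.1.1 gives the whole method for the secondary PFS endpoint: "The nonparametric Kaplan-Meier method will be used to estimate median PFS". Section 9.5.2.4 adds an exploratory question, "whether median PFS is different with patients with mutations in" CDKN2A compared with patients without them.

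Section 4.4.8 sets the imaging: "Response evaluation will occur every 8 weeks (regardless of treatment cycle) and at the final visit", the latter only if there was no scan in the last 4 weeks. Section 4.4 allows each scan to move 7 days either way.

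Section 9.5.1 fixes the design rates: "The null hypothesis is that the PFS rate at 8 weeks is 25" percent, "versus an alternative hypothesis that the rate is 50% or higher". The interim rule is: "If 3 or more (out of 11) patients are progression free the trial will continue with an additional 15 patients being enrolled". Success needs 10 of 26.

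On what counts as an event, section 2.5.1 includes death from any cause, section 9.4.2.1 censors a patient who dies on study, and section 7.4 counts clinical progression and death from progression. I found no rule for dating progression and no interval-censored or sensitivity analysis.

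**The concern.** Progression seen on a scan happened some time since the previous scan. Kaplan-Meier on scan dates treats the scan day as the event day. That matters little when the median spans several scan intervals. Here the design's own rates put the median at or before the first scan, so the estimate can simply reproduce the scan calendar. A trial with 3 of 26 progression-free at week 8 (failure) and one with 10 to 13 of 26 (success) could both report a median of about 8 weeks. The CDKN2A comparison of medians is exposed in the same way, in smaller groups.

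**Working it through.** **1. The plan's own design reproduces.** Inputs from sections 9.3 and 9.5.1: 25% against 50%, stop if 2 or fewer of 11, reject if 9 or fewer of 26. The exact two-stage binomial calculation gives one-sided alpha 0.0857 and power 0.9005, within the stated 0.1 and 90%. The documents give no expected value or precision for median PFS.

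**2. True median under the null.** S(8) = 0.25 is below one half, so the median is before week 8 for any hazard shape. Its position needs an assumption.
- Constant hazard: 8 × ln 2 / (−ln 0.25) = 8 × 0.693 / 1.386 = 4.0 weeks.
- Weibull with shape k and S(8) = 0.25: 8 × 0.5^(1/k), which gives 2.97 (k = 0.7), 5.04 (1.5), 5.66 (2) and 6.35 (3).
- Under the alternative, S(8) = 0.50 puts the median at 8.0 weeks for every shape.

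**3. Every event dated at a scan, no window.** The Kaplan-Meier median (first time the curve is at or below 0.5) is 8 weeks if 13 or fewer of 26 are progression-free at week 8, and later otherwise, in practice 16.
- Null: P(X ≤ 13 | 26, 0.25) = 0.998.
- True rate 35%: 0.962.
- Alternative: P(X ≤ 13 | 26, 0.50) = 0.577, leaving 0.423 for a later median.

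**4. Some events dated when they occur.** Simulation with n = 26, constant hazard, scan window ±7 days, 2,500 trials per scenario; f is the share of events dated exactly.

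| f | Null: typical estimate (weeks) | Null: in weeks 7-9 | Alternative: typical estimate (weeks) | Alternative: in weeks 7-9 | Alternative: above 12 weeks |
|---|---|---|---|---|---|
| 0 | 8.30 | 0.999 | 8.94 | 0.572 | 0.428 |
| 0.2 | 8.13 | 0.999 | 8.88 | 0.602 | 0.314 |
| 0.4 | 7.85 | 0.984 | 8.82 | 0.630 | 0.223 |
| 0.5 | 7.63 | 0.907 | 8.78 | 0.641 | 0.172 |
| 0.6 | 7.34 | 0.725 | 8.66 | 0.669 | 0.133 |
| 0.75 | 5.86 | 0.316 | 8.49 | 0.608 | 0.094 |
| 1 | 3.80 | 0.009 | 7.46 | 0.337 | 0.039 |

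**5. The rule on deaths matters.** If early deaths are censored, as section 9.4.2.1 says, and make up 10% to 30% of events, the null estimate stays at 8 weeks (above 12 weeks in 0.5% to 3.8% of trials). The alternative moves above 12 weeks in 57% to 77%.

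**6. CDKN2A groups.** Assume 13 per group, true 8-week rates of 15% and 40%, and scan-dated events; none of these is in the documents. Constant-hazard medians are 2.9 and 6.1 weeks. A group's median reads 8 weeks if 6 or fewer of 13 are progression-free: probability 0.999 and 0.771. Both read 8 weeks in 0.999 × 0.771 = 0.77 of trials.

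**7. Limits of a parametric replacement.** An interval-censored exponential fit recovers the median when the data are exponential. With Weibull data under the null it does not: about 3.5 weeks against a true 5.7 (shape 2), and about 4.7 against a true 3.0 (shape 0.7). A fitted Weibull at n = 26 ranges from about 1.6 to 6.8 weeks around a true 4.0.

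**The case against.** The strongest reply is that scans are not the only source of event dates. Visits are every 2 weeks up to week 8, clinical progression counts under section 7.4, and leaving the study triggers a tumor assessment. If 60-75% or more of events were dated this way, most of the bias would go. That stands. The documents do not give the share.

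Three stronger readings are tempting, and the documents do not support them.
- A reader might infer that the median carries no information. It does carry some: with scan-dated events a result near 16 weeks occurs in about 42% of alternative trials and about 0.2% of null trials.
- A reader might take 4 weeks as the trial's own null median. The documents fix only the 25% rate; 4 weeks needs a constant hazard.
- A reader might infer that the estimate would flatter the regimen beside the 1.5-month median quoted for 5-FU in section 1.5.2. That is second-line background. No comparison with it is planned, and its scan schedule is not given.

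It is also fair that median PFS is secondary, that the CDKN2A analysis is labelled exploratory, and that a parametric median inside the first interval is driven by the model (step 7). This argues for an interval-censored analysis as sensitivity, not as the main estimate.

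**Conclusion.** The point holds in limited form. Under the null, a Kaplan-Meier median on scan dates is biased upward, from a true value below 8 weeks to about 8. It stays there in over 98% of trials with up to about 40% of events dated between scans. A reported median near 8 weeks does not separate null from alternative (0.998 against 0.58 with all events scan-dated); one near 16 weeks does. The direction of the bias needs no hazard assumption, but its size does. All of it rests on progression being dated mainly at scans, which the plan neither states nor excludes. The go/no-go test on the 8-week proportion is not affected, so this is a low-cost correction to a secondary result and an exploratory comparison.

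**What to change.** - **Section 9.5.2.1.1:** keep Kaplan-Meier and state how progression is dated. If half or more of the patients have progressed by the first scan, report the median as *8 weeks or less*, with the 8-week PFS rate and its confidence interval (the synopsis already plans an exact 95% interval for that rate).
- **Sensitivity analysis:** add an interval-censored analysis with progression placed between the last progression-free scan and the scan showing PD. State the parametric assumption and show more than one shape.
- **Section 9.5.2.4:** compare CDKN2A groups on the proportion progression-free at 8 weeks, or with an interval-censored model, instead of on medians.
- **Sections 2.5.1 and 9.4.2.1:** reconcile the two rules on deaths, and check section 7.4 against the result. Any PFS analysis needs one rule, and step 5 of the working shows that the choice moves the median.

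The cost is plan wording and a little more analysis on data already collected, with no change to visits, scans or sample size. The downside is that any point estimate inside the first interval depends on a parametric form, which is why it stays a sensitivity analysis.

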4.4 Detailed Patient Assessments

Subject assessments (physical examinations, vital signs, performance status, chemistry, hematology, medication review, and adverse event evaluations) will be conducted at screening, Cycle 1 Day 1, every 2 weeks thereafter until the first response assessment at 8 weeks, and then every 4 weeks thereafter. Study visits and the on-treatment tumor biopsy may be performed 3 days before or after the scheduled date due to unforeseen or unavoidable circumstances, and attempts should be made to schedule visits to line up with the start of a new cycle (within the constraints of the above parameters). Study drugs will be dispensed at the last visit prior to the start of the next 28 day cycle. The radiologic first response assessment at 8 weeks, and subsequent radiologic response assessments every 8 weeks thereafter, may be performed up to 7 days before or after the scheduled date due to unforeseen or unavoidable circumstances. Details are provided in Table 5, and a checklist highlighting the important events for screening through the completion of the trial is provided below, as Table 6.

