7.4 Definition of Disease Progression

Disease progression will be defined as:

- 1) Radiologic progression of disease by RECIST v1.1 criteria.
- 2) Clinical progression as determined by the investigator, which may be characterized as, but is not limited to:
 - a. Increase of at least 2 points in ECOG performance status attributable to cancer progression.
 - b. Requirement for palliative radiation, chemotherapy or surgery.
- 3) Death from disease progression

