8.2 Mutational Analysis of Tumor Samples

Pre-treatment biopsy samples will be used for targeted next generation sequencing using a panel that includes 196 genes commonly altered in cancer with a specific emphasis on genes that are altered in pancreatic cancer. This platform will allow >500x coverage across the genes and provide both single nucleotide variant and copy number information. Each common gene mutation will be evaluated for association with PFS. The presence of a *CDKN2A* mutation or deletion will be correlated with PFS, given the hypothesis that derangement in this pathway results in p16 loss, creating a therapeutic target of CDK4/6 (naturally inhibited by p16).

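### The CDKN2A comparison in 9.5.2.4 rests on median PFS, which 8-weekly scans make a coarse measure; a Cox or log-rank analysis, as planned next door for the IHC markers, would use the data better

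*Combined protocol and SAP*

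**What the plan says.** - **CDKN2A analysis (9.5.2.4).** The sequencing work "will examine whether median PFS is different with patients with mutations in" CDKN2A compared with patients without them. No test, model, effect measure or confidence interval is given. The same item states that "NGS analysis is also exploratory in nature".
- **Sequencing section (8.2).** "Each common gene mutation will be evaluated for association with PFS", and CDKN2A mutation or deletion is to be correlated with PFS. No method is named here either.
- **IHC markers (9.5.2.3).** "Cox proportional hazard regression models will be fit to determine whether these secondary endpoints are associated with PFS".
- **Imaging (4.4.8 and 4.4).** "Response evaluation will occur every 8 weeks (regardless of treatment cycle) and at the final visit"; scans "may be performed up to 7 days before or after the scheduled date due to unforeseen or unavoidable circumstances".
- **Progression (7.4).** Besides RECIST progression it includes "Clinical progression as determined by the investigator, which may be characterized as, but is not limited to" a worsened performance status or a need for palliative treatment.
- **Design rates (9.5.1 and 9.3).** PFS at 8 weeks is 25% under the null and 50% under the alternative, with 26 evaluable patients.

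**The concern.** Most progressions are found at scheduled scans, so most PFS times cluster near weeks 8, 16, 24 and so on. With 25–50% of patients progression-free at the first scan, a group median sits at that scan or soon after it. Comparing two medians uses one point of each curve. How long the longer-lasting patients remain progression-free cannot influence it, and one patient's result can move a small group's median by a whole scan interval.

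CDKN2A loss is central to the trial's rationale, and 8.2 states a hypothesis linking it to benefit. A reader shown 8 weeks against 8 weeks could conclude that the alteration does not matter when it had halved the hazard. The plan already uses a fuller method one item earlier.

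**Working it through.** **The plan's own figures.** The documents give no sample size, effect or power for this comparison. The design that supplies the 25% and 50% rates does reproduce. With 11 then 26 patients, continuing on 3 or more and succeeding on 10 or more, the exact one-sided alpha is 0.0857 (0.1 stated) and the power is 0.9005 (90% stated).

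**Inputs from the documents.** Scan interval 8 weeks (4.4.8); window ±7 days (4.4); 8-week PFS 25% or 50% (9.5.1); 26 evaluable patients (9.3).

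**Assumptions.** Exponential PFS; hazard ratio 0.5 in favour of the mutated group; all 26 patients have an event; progression dated at the next scheduled scan; mutated share 30%, 50% or 70% (8, 13 or 18 of 26); two-sided 5% tests. The hazard ratio equals the plan's treatment contrast, ln(0.50)/ln(0.25) = 0.693/1.386 = 0.5. The documents give neither a marker effect nor a CDKN2A percentage.

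**Step 1: chance that both medians come from the same scan.** If a group's 8-week PFS is S, a patient has progressed by scan k with probability 1 − S^k. The Kaplan-Meier median is at or before scan k when at least half of the group has progressed by then. Halving the hazard turns S into √S.

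Worked case, 13 against 13, unmutated group at 25%:
- Unmutated: 75% have progressed by scan 1. P(at least 7 of 13) = 0.976, leaving 0.024 for scan 2.
- Mutated: √0.25 = 0.50. P(at least 7 of 13) = 0.500 for scan 1. By scan 2, 75% have progressed, so scan 2 has 0.976 − 0.500 = 0.476.
- Same scan: 0.976 × 0.500 + 0.024 × 0.476 = 0.488 + 0.011 = 0.499.

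| Unmutated group, PFS at 8 weeks | 30% mutated | 50% mutated | 70% mutated |
|---|---|---|---|
| 25% | 64% | 50% | 59% |
| 50% | 29% | 25% | 22% |

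Simulation of 2,000 trials per cell gave 63%, 51%, 58% and 30%, 26%, 20%.

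**Step 2: sensitivity.**
- If scan dates spread evenly over ±7 days, exactly equal medians fall to about 1.5–6% of trials. The share of trials in which both medians come from the same scan does not change.
- If 20% of events are dated off-scan, exact equality is 49–63% (unmutated group at 25%) or 15–20% (at 50%). If 40% are off-scan, it is 46–55% or 9–14%.
- If the 25% or 50% rate is read as the rate for all patients together, the same-scan figures become 79–97% or 27–37%. Averaging the two middle values in even-sized groups lowers these to 55–92% or 15–27%.

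**Step 3: power.** The Schoenfeld approximation is Φ(√(d·p(1−p))·|ln HR| − 1.96) with d = 26 events and mutated share p.
- p = 0.5: √6.5 × 0.693 = 1.767; 1.767 − 1.96 = −0.193; power 42%.
- p = 0.3 or 0.7: √5.46 × 0.693 = 1.620; 1.620 − 1.96 = −0.340; power 37%.

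Simulated on the 8-week grid, where ties and small groups cost something:

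| Method | Power |
|---|---|
| Log-rank / Cox score test | about 26–39% |
| Chi-square median test | 21–31% |
| Exact median test | 13–17% |

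**Step 4: what the better method still lacks.** For 80% power at this hazard ratio, 66 events are needed at a 50% share and 78 at 70%.

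**The case against.** Several stronger readings are tempting, and the documents do not support them.

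- **That the rest of the PFS curve is thrown away.** This describes 9.5.2.4 read alone. Section 8.2 speaks of correlating CDKN2A status with PFS as such. The plan is inconsistent and incomplete on method, not plainly confined to the median.
- **That the medians will be identical.** Exact ties need nominal scan dates. The ±7-day window, final-visit imaging and clinical progression break them. What persists is that both medians come from the same scan, and with the unmutated group at 50% that is a minority of trials.
- **That half the power is lost.** The plan names no test. Within the simulated settings the exact median test keeps 44% to 51% of the log-rank power (0.152/0.346 to 0.132/0.261), but the chi-square version keeps 64% to 86% (0.218/0.338 to 0.296/0.346). A permutation test on the difference in medians does worse still, at about 0–8% power for 50–70% mutated.
- **That an important trial result is at risk.** The analysis is labelled exploratory and no decision uses it. Section 8.1.2 names RB, cyclin D1 and p16 as possible predictive markers, and 9.5.2.3 already covers p16, the CDKN2A product, with Cox models.

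The inputs are also open to challenge. The hazard ratio is borrowed from the treatment hypothesis. The number 26 is an assumption: 9.5.2.4 is not limited to Phase II, up to 44 patients may be accrued (9.3), and biopsies are sought from all. In the other direction, biopsies can be waived for undue risk, and sequencing comes second when tissue is short (8.4).

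These points limit the claim without removing it. If the comparison of medians was shorthand for a log-rank test, the plan does not say so, and it does name Cox where it wants Cox.

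**Conclusion.** The point holds as a minor improvement to the choice of analysis. Followed as written, 9.5.2.4 gives a less informative answer than the method already specified in 9.5.2.3. Under the assumptions listed, the medians share a scan in roughly half to two-thirds of trials with the unmutated group at 25%, and in roughly a fifth to 30% with it at 50%. Log-rank or Cox power is about 26–39%; the two standard median tests lie between 13% and 31%. These figures depend on the assumed hazard ratio, mutated share, number of patients and absence of censoring, so they show the direction and rough size of the loss only. Under either method a null result would say little about CDKN2A.

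**What to change.** In 9.5.2.4, replace the comparison of medians with a Cox regression of PFS on CDKN2A status, tested by the score or log-rank test with exact handling of ties, and report the hazard ratio with its 95% CI. Keep Kaplan-Meier medians by group as description. Refer to the same method in 8.2 so that the two sections agree. An interval-censored or discrete-time model is a reasonable sensitivity analysis.

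While editing, settle how deaths enter PFS: 2.5.1 counts death from any cause as an event, whereas 9.4.2.1 also censors patients who die on study. Any PFS comparison depends on this.

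The cost is one sentence in 9.5.2.4 and a cross-reference in 8.2, with no new patients, data or procedures. The exploratory label stays.
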